Appendix IV. Microfinance data collection instruments

Harambee Survey Assessment Tool (PID: 580) 07/29/2024 9:27pm

#	Variable / Field Name	Field Label Field Note	Field Attributes (Field Type Validation, Choices, Calcul	•			
Inst	Instrument: Meta-Data (metadata) [collapsed]						
Inst	rument: Responden	t Demographics (respondent_demographic	5)	[collapsed]			
Inst	rument: Health Insu	rance (health_insurance)		[collapsed]			
Inst	rument: OSLO Socia	Support Scale -3 (oslo_social_support_scal	e_3)	[collapsed]			
	•	edical Outcomes Study HIV Health Surv mes_study_hiv_health_survey_m)	ey (MOS-HIV)	[collapsed]			
Inst	rument: Patient Hea	alth Questionnaire-2 (patient_health_ques	tionnaire2)	[collapsed]			
	-	CTG Self Report Adherence d_actg_self_report_adherence_questionnaire)		[collapsed]			
		onadherence (DOSE-Nonadherence) of_nonadherence_dosenonadherence_question	nna)	[collapsed]			
Inst	rument: Barriers to	Accessing Care (barriers_to_accessing_care))	[collapsed]			
Inst	rument: Patient Sat	isfaction Survey (patient_satisfaction_surve	ey)	[collapsed]			
Inst	rument: Felt Stigma	Questionnaire (felt_stigma_questionnaire)		[collapsed]			
	rument: Household ousehold_food_insecur	Food Insecurity Access Scale (HFIAS) ity_access_scale_hfias)		[collapsed]			
Inst	rument: Household	Economic Status (household_economic_sta	tus)	[collapsed]			
Inst	rument: Employmer	nt and Income Status (employment_and_in	come_status)	[collapsed]			
Inst	rument: HTN/DM Sc	reening Form (htndm_screening_form)		[collapsed]			
Inst	rument: GISHE Indiv	vidual Record Form (gishe_individual_record	d_form)				
182	<pre>[nature_of_encounter _visit]</pre>	1. Nature of encounter	radio 1 Initial visit 2 Recurrent visit				
402		Continue Hooders (NIDWO) (ALL MEMBER DATA (DATA VA	Custom alignment: RH				
183	[gishe_id_number]	Section Header: INDIVIDUAL MEMBER DATA (DATA YA MWANACHAMA) (to be completed for each individual member of the group) (Kila mwanachama ajaziwe data yake)	text				
		2. GISHE/Chamaa/MF Group ID Number (Nambari ya Kikundi)					
184	[phone_number]	3. Current Phone number (Nambari ya simu)	text (number, Min: 0)				
185	<pre>[date_first_join_gro up]</pre>	4. When did this individual first join a GISHE/Chamaa/MF group	text (date_dmy)				

	Show the field ONLY i f: [nature_of_encounter_ visit] = '1'	(Je, mara ya kwanza mwanakikundi huyu kujiunga na kikundi ilikuwa lini)			
186	<pre>[total_share_contrib uted] Show the field ONLY i f: [nature_of_encounter_ visit] = '1'</pre>	5. Total amount of shares contributed in this current GISHE/Chamaa/MF group (Jumla ya hisa (pesa) alizochanga katika kikundi hiki cha sasa)	tex	t (integer, Min: 0, Max: '	100000)
187	[outstanding_loan_ba 1] Show the field ONLY i f: [nature_of_encounter_ visit] = '1'	6. Total outstanding loan balance in this current GISHE/Chamaa/MF group (Jumla ya pesa za mkopo alizonazo katika kikundi hiki cha sasa)	tex	ct (integer, Min: 0, Max: 1	100000)
188	<pre>[no_of_meetings_atte nded] Show the field ONLY i f: [nature_of_encounter_ visit] = '2'</pre>	Section Header: RECCURENT DATA 7. Number of meetings attended during last period (Nambari ya mikutano uliyohudhuria kwa musimu uliopita)	tex	t (number, Min: 0, Max:	60)
189	[total_shares_purcha sed] Show the field ONLY i f: [nature_of_encounter_ visit] = '2'	8. Total number of shares purchased during the last period (Jumla ya hisa zilizonunuliwa msimu uliopita)	text (integer, Min: 0, Max: 100000) text (integer, Min: 0, Max: 100000)		100000)
190	[loans_disbursed] Show the field ONLY i f: [nature_of_encounter_ visit] = '2'	9. Total amount of loans disbursed during the last period (Jumla ya mikopo iliyochukuliwa msimu uliopita)			100000)
191	<pre>[loan_bal_outstandin g] Show the field ONLY i f: [nature_of_encounter_ visit] = '2'</pre>	10. Total loan balance outstanding on current date (Jumla ya mikopo ambazo hazijalipwa hadi sasa)	tex	ct (integer, Min: 0, Max: 1	100000)
192	[purpose_for_loan] Show the field ONLY i f: [nature_of_encounter_ visit] = '2' and [loans_d isbursed] <> "	11. For what purpose did this member use the borrowed funds during the last period (Je, mwanachama alitumia pesa alizokopa msimu uliopita kufanya nini)	che 1 2 3	purpose_for_loan2 purpose_for_loan2	inputs such as seeds, ox plough

					for children
			4	purpose_for_loan4	To pay for medical expenses (health insurance, medical fees, medication
			5	purpose_for_loan5	To trade ar invest in small business
			6	purpose_for_loan6	To repair shelter or homestead
			7	purpose_for_loan7	To buy clothing fo self and family
			8	purpose_for_loan8	Other
	[other_use_of_loan] Show the field ONLY i f: [purpose_for_loan(8)] ='1'	11a. If other use of loan specify	tex		
194	[use_social_fund]	this period (Je, mwanachama alitumia pesa za mfuko wa jamii katika msimu uliopita)	radio		
	Show the field ONLY i		1 Yes- Granted, no payment		
	f: [nature_of_encounter_ visit] = '2'		3	Yes- Borrowed with re	payment
			Cu	stom alignment: RH	
195	[funds_repaid_during	12a. If yes, borrowed with repayment, were the	yes	sno	
	_period]	funds repaid during this period	1	Yes	
	Show the field ONLY i f:	ziiiipwa kwa msimu nuo)	0	No	
	[use_social_fund] = '2'		Cu	stom alignment: RH	
196	[social_fund_without	12b. If yes- granted with no repayment, what	dro	pdown	
	_repayment]	was the reason for using the social fund (Kama ni ndio, je pesa za mfuko wa jamii	1	1.Bereavement/Funera	
	Show the field ONLY i f:	zilitumika kufanya nini)	2	2. Hospital/Medical fee	es
	[use_social_fund] = '1'		4	School fees Celebration (birthda	ıy, baby
				shower)	

			6 6. Other
197	[other_reason_for_so cial_fund] Show the field ONLY if: [social_fund_without_repayment] = '6'	12c. If other reason, specify (Kama ni nyingine, taja)	text
198	[defaulted_since_las t_encounter] Show the field ONLY i f: [nature_of_encounter_ visit] = '2'	13. Has this individual defaulted during the last encounter (Je mwanachama huyu amakosa kulipa mkopo wake tangu mara ya mwisho mlipokutana)	yesno 1 Yes 0 No Custom alignment: RH
199	[reasons_defaulted] Show the field ONLY i f: [defaulted_since_last_ encounter] = '1'	13a. If defaulter, give reasons for defaulting (Kama ni ndio, je ni jambo lipi lilimsababisha kutolipa mkopo)	checkbox 1 reasons_defaulted1 No longer attending meetings 2 reasons_defaulted2 No longer abl to contribute/sh 3 reasons_defaulted3 Emergency (Family, health death) 4 reasons_defaulted4 Defaulted on loan 5 reasons_defaulted5 Other
200	[other_reason_defaul ted] Show the field ONLY i f: [reasons_defaulted(5)] = '1'	13b. If other reason for defaulted, specify (Kama ni nyingine, taja)	text Custom alignment: RH
201	<pre>[time_interview_ende d]</pre>	Section Header: We are now finished with this survey. Thank you for taking the time to speak with me today. All of your responses will remain private and the information you shared will help us during this study. Do you have any questions? Thank you very much. (Sasa, tumetamatisha mahojiano haya. Asante kwa kuchukua muda wako kuzungumza nami leo. Majibu yako yote yatabaki kuwa ya siri na habari ulizoshiriki zitatusaidia katika utafiti huu. Je, unayo maswali yoyote? Asante sana. 14. Time interviewed ended (Wakati mahojiano yalikamilika)	text (time)
202	<pre>[gishe_individual_re cord_form_complete]</pre>	Section Header: Form Status Complete?	dropdown 0 Incomplete 1 Unverified 2 Complete

	encounter, _	kikamilifu ni wale ambao huhudhuria mikutano ya Chamaa mara kwa mara na	
		hulipa fedha za hisa/kusaidia katika janga)	 
16	<pre>[date_of_last_encou nter]</pre>	Section Header: The following questions refer to the data collection period starting from the last encounter when the form was collected to the present. (Maswali yafuatayo	text (date_mdy)
	Show the field ONLY if:	yanahusiana na wakati wa ukusanyaji wa ujumbe (deta) kuanzia mara ya mwishofomu ilipojazwa hadi sasa)	
	[nature_of_encounte r] = '2'	12. Date of last encounter when form was collected (Tarehe ambayo fomu ilijazwa mara ya	

17	<pre>[number_of_meeting s] Show the field ONLY if: [nature_of_encounte r] = '2'</pre>	13. How many meetings took place during the data collection period (Je, ni mikutano mingapi zilifanywa wakati wa ukusanyaji wa ujumbe)	text (number, Min: 0, Max: 15)
18	[meet_as_a_group] Show the field ONLY if: [nature_of_encounte r] = '1'	Section Header: GROUP PROCESS (Mchakato wa kikundi) 14. How often do you meet as a group (Je, huwa munakutanamara ngapi lama kikundi)	radio 1 Weekly (Kila Wiki) 2 Bi-monthly (Baada ya wiki mbili) 3 Monthly (Kila Mwezi) 4 Quarterly (Baada ya miezi tatu) 5 Other (Nyingine)
19	<pre>[meet_as_a_group_sp ecify] Show the field ONLY if: [meet_as_a_group] = '5'</pre>	14a. How often do you meet as a group, other specify: (Je, huwa munakutanamara ngapi lama kikundi, nyingine, bainisha):	text
20	[registration_fee] Show the field ONLY if: [nature_of_encounte r] = '1'	13. Registration fee amount (Fedha ya kujiandikisha katika kikundi)	text (integer, Min: 0, Max: 20000)
21	[social_fund_value] Show the field ONLY if: [nature_of_encounte r] = '1'	14. Single social fund value (Fedha ya kusaidia katika janga)	text (integer, Min: 0, Max: 20000)
22	[single_share_valu e] Show the field ONLY if: [nature_of_encounte r] = '1'	15. Single share value (Thamani ya hisa moja)	text (integer, Min: 0, Max: 20000)
23	[gishe_group_record _form_complete]	Section Header: Form Status Complete?	dropdown 0 Incomplete 1 Unverified 2 Complete

Appendix VI: KEY INFORMANT INTERVIEW GUIDE – PARTICIPANTS

Introduction: Review the study procedures and details with participant, including audio recording, confidentiality, and rights to refuse participation. Obtain informed consent.

Because you are a patient of an AMPATH clinic, we want to learn about your experience receiving HIV and primary care through AMPATH. (If the participant is also in a microfinance group, you can also say that you want to learn about their experience as a microfinance group member.) We also want to hear about some of the challenges you face in getting care and about what would help you to receive the care your need on a regular basis.

Please remember that anything you say during this interview will be not be shared with anyone at AMPATH or in the community.

I. Socio-demographic:

- a) Age in years
- a) Gender
- b) Most recent visit to AMPATH clinic and reason for visit
- c) Time has been a member of a microfinance group (for trial participants)

II. ART adherence barriers and facilitators

The intent of this portion of the agenda is to explore participant's self-reported barriers/facilitators to accessing HIV care, including household economic conditions, food security, geography/distance, social support, and HIV-related stigma.

- 1. **Lead question**: What was your biggest concern when you found out you were HIV positive and started ART?
- 2. Follow-up question: Do you take your ART medication as indicated? What are some reasons why you do not or have not taken your ART medication as indicated, meaning as often or as much as told by medical personnel?
- 3. Follow-up question: When you WANT to stay adherent ART, what gets in the way?
 - a. Medication/regimen: How does the medication experience (side effects, schedule, dosing) affect your ability to take ART as prescribed?
 - b. Patient factors:
 - i. Probe: developmental hallmarks such as family responsibility
 - ii. Probe: specific challenges relating to mental health
 - c. Peer, partner, family factors
 - i. Probe: Support (or lack of support) from family, friends, clinicians, others
 - ii. Probe: Does HIV stigma affect your decision to take ART? How? (explore covert ART use and concerns over inadvertent disclosure)
 - d. Clinician factors
 - i. Probe: positive and negative provider attitudes for clinical needs of people living with HIV
 - ii. Probe: differences (if any) in experience between clinical care environments (e.g., different clinics, different regions)
 - e. Structural factors: What about living in your community makes it easy or hard for you to take ART as prescribed?
 - i. Probe: Transport, food security, housing, migration

f. **Lead question**: What helps you to STAY adherent to ART? "Adherent" means taking medication as often and/or as much as told by medical personnel.

III. Acceptability of receiving NCD/HIV integrated care in the community via microfinance groups

The intent of this portion is to introduce the idea of delivering NCD/HIV integrated care in the community via microfinance groups and to explore the acceptability ICB as a strategy for supporting better ART adherence in people living with HIV.

- 1. **Lead question**: We want to understand what you think about using microfinance groups to help people improve adherence to ART. By adherence we mean taking ART as prescribed. Do you think you and other people who are living with HIV would like to receive NCD/HIV care in the community when they attend a microfinance group meeting?
- 2. **Lead**: Can you tell us about how to design this type of health care service so that it supports adherence to ART among people who are living with HIV?
 - a. How should the NCD/HIV care be DELIVERED to people in the community (e.g., to individuals privately, to a group of people trying to adhere)?
 - b. How OFTEN should NCD/HIV service be delivered in the community (e.g., at every microfinance group meeting, at the payout meetings, monthly, quarterly?)
- 3. Follow-up question: To make sure you and other people who are living with HIV have all the support they need to adhere to ART, should NCD/HIV care be delivered on its own or in combination with other programs (such as motivational support, education on why adherence is important and how to adhere, or group/peer support groups for adherence)?

Closing: Thank participant for their time. Remind participant about the confidentiality of the interview. Ask if they have any questions about anything that was discussed.

EXAMPLE: Thank you for your time and for sharing your thoughts with us. We want to remind you that your comments will remain confidential. Do you have additional questions or comments?

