For **qualitative mediation analyses**, we will conduct qualitative in-depth with 40 participants from the Aim 1 randomized controlled trial (n=20 from the MF+ICB arm and =20 from the MF+SOC arm). Following the Aim 1 trial's 18-month assessment, research assistants will provide information to a purposively selected sample of n=40 participants and invite them to join the qualitative data collection. Following the Aim 1 trial's 18-month assessment, research assistants will also invite n=10 current AMPATH staff who delivered the intervention to participate in in-depth interviews. Individuals who are interested in participating in the Aim 2 interviews will complete the informed consent form in Appendix V.

- 8.1.1 Inclusion criteria for trial participants:
 - consented to participate in the intervention study (Aim 1) and completed at least the baseline and 18-month assessment;
 - participated in at least 2 MF group meetings during the study period; and
 - able and willing to provide informed consent for the qualitative study.
- 8.1.2 Inclusion criteria for key stakeholder and care providers:
 - Delivered care in the intervention arm of the trial for at least 6 months;
 - 18 years of age or older; and
 - Able and willing to provide informed consent to participate.

Data for all Aim 1 participants (n=900 microfinance groups + 300 SOC) collected via the survey measures (Appendix III) administered at baseline, 9-month, and 18-month follow-up visits will be used for the Aim 2 quantitative mediation analyses.

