8.2 Aim 2 (mixed methods mediation analysis) procedures

In depth interviews (IDIs) with trial participants will take place in a private and quiet location with the use of an interview guide. A semi-structured guide (Appendix VI) will include questions to assess the following domains: 1) Experiences related to MF groups, 2) Barriers/facilitators to accessing HIV care, including household economic conditions, food security, geography/distance, social support, and HIV-related stigma; 3) How participation in MF and/or community-based care impacts retention in care,

adherence to ART; 4) Satisfaction with HIV care delivery (community-based or facility-based); 5) Suggested improvements for care delivery models.

In depth interviews (IDIs) with intervention delivery personnel will take place in a private location, outside of their work location if preferred. Interviewers will be trained members of the AMPATH social behavioral team. Semi-strucutred interview guides (Appendix VII) with staff will focus on the following domains: 1) Satisfaction with job; 2) Challenges to delivering HIV care in the community; 3) Suggested improvements; 4) Context-specific issues delivering care in this setting related to geography, community, etc. Interviews will be conducted in Swahili or English by a trained member of the research staff and audio-recorded with permission. All interviews will be transcribed and translated in full. Transcriptions will be entered into a text organization software program for analysis.

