Appendix VII: KEY INFORMANT INTERVIEW GUIDE – PROVIDERS

Introduction: Review the study procedures and details with participant, including audio recording, confidentiality, and rights to refuse participation. Obtain informed assent/consent.

AMPATH oversees over 1,300 microfinance groups, with 48 of these groups composed of only members living with HIV. AMPATH has begun to deliver chronic disease care, mainly for hypertension and diabetes, in a community-based group setting to those participating in microfinance groups. Our aim is to investigate whether it is feasible to adapt this model of group-based care delivery to address the needs of people living with HIV in microfinance groups.

We want to gather your thoughts on community-based care models, the strengths and challenges of integrating care, and the considerations that must be made when delivering HIV care outside of the health facility. We are particularly interested in your experience delivery NCD/HIV care to via microfinance groups through your role as a (insert job title).

A. Socio-demographic:

- a) Age in years
- a) Gender
- b) Health provider cadre
- c) Length of time working at AMPATH

B. Warm-up:

1. Tell me about yourself and your role within the AMPATH program **Probes:** Can you describe a normal working day for you?

Perception about patient involvement in community-based groups

2. What is your perception about community-based groups?

Probes:

- Perception about social support groups?
- Perception about microfinance groups? E.g chamaz, merry-go-rounds
- 3. Do you know of any patient(s) in your clinic in any kind of community-based financial group(s)? If **NO** move to next question

If **YES** continue with probes

Probes:

- Provide a small description about the group(s)
- What is the role of the group(s)?
- How are patients in these groups different from patients who are not in any group?
- 4. What do you think about patient's participation in community-based financial group(s) (including GISE, chama cha mama toto, joywo)?

Probes:

- What are the advantages of patients participating in community-based financial groups? (explore positive aspects on social, economic and health outcomes)
- What are the disadvantages of patients participating in community-based financial groups? (explore negative aspects on social, economic and health outcomes)

Perception about care delivery beyond the health facility

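### The Aim 2 participant guide has no direct question on three of its five stated domains and presents community care as a new idea after month 18, so the qualitative mechanism question is addressed only indirectly

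*Combined protocol and SAP*

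**What the plan says.** **Timing and sample (section 8.1).** "Following the Aim 1 trial's 18-month assessment, research assistants will provide information to a purposively selected sample of n=40 participants". Section 8.1.1 confirms the timing: eligible participants have "consented to participate in the intervention study (Aim 1) and completed at least the baseline and 18-month assessment". The sample is "n=20 from the MF+ICB arm and =20 from the MF+SOC arm". On the provider side, "research assistants will also invite n=10 current AMPATH staff who delivered the intervention", and section 8.1.2 requires at least 6 months of delivery.

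**Content promised (section 8.2).** Appendix VI is to hold questions on five domains: (1) experience in microfinance groups; (2) barriers and facilitators to HIV care; (3) "How participation in MF and/or community-based care impacts retention in care", together with ART adherence; (4) satisfaction with community or facility delivery; (5) suggested improvements. The staff guide has four domains, of which job satisfaction is the first.

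**Use (section 8.3).** The coded text is to identify how microfinance and community care acted on retention and adherence, to contrast the two arms on the added benefit of community care, and to help explain the quantitative mediation results.

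**The guides.** Appendix VI part II asks about ART adherence. The stated intent of part III begins: "The intent of this portion is to introduce the idea of delivering NCD/HIV integrated care in the community via microfinance groups". The introduction to Appendix VII states: "Our aim is to investigate whether it is feasible to adapt this model of group-based care delivery".

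**The concern.** The guides read like acceptability tools written before an intervention starts, yet they are scheduled for people who have finished the trial and staff who delivered the care. Part III of Appendix VI asks whether people would want community care, how it should be designed and how often it should be given. For Arm A these are questions about something already experienced, put as if it had not happened.

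Domain 3 is the mechanism question of section 8.3. If the guide does not ask it, the transcripts will contain what participants volunteer about it and no systematic account. The contrast between arms, and the use of the interviews to explain the mediation analysis, would then rest on inference from answers to other questions.

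**Working it through.** No effect size or power figure is involved. The one number to reproduce is the interview total: 20 (MF+ICB) + 20 (MF+SOC) + 10 (staff) = 50, which agrees with section 8.3.

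The check sets each participant domain in section 8.2 against every question and probe in Appendix VI.

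- **Domain 1, microfinance experience: no direct question.** Nearest items: an optional line in the introduction, and length of membership among the demographics. The introduction treats membership as conditional, although all 40 interviewees come from microfinance arms.
- **Domain 2, barriers and facilitators: covered.** Part II probes support, stigma, transport, food security, housing and migration. Household economic conditions appear in its stated intent but have no probe of their own. The framing is ART adherence rather than access to care.
- **Domain 3, effect on own retention and adherence: no direct question.** Nearest item: part III item 1, a general opinion on using microfinance groups to support adherence. No question concerns retention. The date and reason of the latest clinic visit are recorded as demographics, and the introduction mentions receiving care regularly, but no question follows from either.
- **Domain 4, satisfaction with delivery: no direct question.** Nearest items: probes on provider attitudes, and on differences between care environments. The latter gives clinics and regions as its examples, not community against facility.
- **Domain 5, improvements: covered**, prospectively, by part III items 2 and 3.

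Result: 2 of 5 domains have direct questions; 3 of 5 have only marginal related items. There is no separate version or branch by arm.

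**Which interviews are affected.** The missing questions affect all 20 + 20 = 40 participant interviews. The framing of part III conflicts with the trial experience of the 20 Arm A interviewees only. The 20 Arm B interviewees received facility care, so prospective wording is not out of place for them.

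**Provider guide.** Job satisfaction has no question. The introduction gives a feasibility aim but also says that experience of delivering the care is of particular interest. Items 5 and 6 are hypothetical. Items 7 to 10 (advantages, challenges, differences from other chronic diseases, conditions for success) can draw on experience and cover the challenge and improvement domains. No numbered item asks directly what happened during delivery.

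**Is the guide superseded?** The addendum lists 11 changes. Item 4 deals with fees and refreshments for the Aim 2 interviews. None revises either guide, so Appendices VI and VII stand as current.

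**The case against.** The strongest reply is that section 8.3 compares coded text between arms, and part II supplies comparable text from both. It asks about participants' own adherence, what gets in the way and what helps, and it probes several of the hypothesised mechanisms. An Arm A participant can answer that receiving care at the group meeting helps, and the arms can then be contrasted. The guide is also semi-structured, so an interviewer may follow up. The survey in Appendix III separately measures barriers to care and satisfaction, at 0, 9 and 18 months in the microfinance arms.

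Most of this stands. A reader might infer that the guide asks nothing on three domains, that the mechanism question is not measured, or that the added effect of community care cannot be coded from the transcripts. The documents do not support any of these: related items exist for each domain, and part II gives indirect evidence on mechanisms. Nor do they support the inference that all interviewees are asked hypothetical questions about care they have had; that conflict does not apply to Arm B.

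What the reply does not remove is the gap between section 8.2 and the guide. Unscripted follow-up is not a plan. Part II does not link barriers to the care received in the trial. The survey records closed ratings, and its satisfaction module is introduced as concerning AMPATH facilities, so it does not explain why community delivery did or did not change attendance.

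**Conclusion.** The point holds in a limited form. Section 8.2 commits to questions on five domains; Appendix VI has no direct question on three of them (1, 3 and 4), in all 40 participant interviews. Part III also conflicts with the 18-month assignment of the 20 Arm A interviewees to community care. Appendix VII omits job satisfaction and frames much of its content as feasibility. The question of how community care affected retention and adherence is therefore addressed indirectly, and for retention only incidentally.

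The consequence is confined to the qualitative part of Aim 2. The primary endpoint, its analysis and the quantitative mediation models are untouched.

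The conclusion assumes that the appendices are the guides in use. It also takes assignment as exposure: section 8.1.1 requires attendance at only 2 or more group meetings, so an individual Arm A interviewee may have had less community care than 18 months implies. Such a participant would still have been assigned to the model that part III presents as new.

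**What to change.** **Appendix VI, both arms.** Keep part III items 2 and 3, which are the main coverage of domain 5; replacing part III outright would lose it. Add retrospective questions on experience in the group, on what changed since month 0 in attending visits and taking ART and why, and on satisfaction with where care was received.

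**Appendix VI, Arm A.** Replace the introductory framing of part III and its item 1 with questions on what the community visits changed compared with facility visits.

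**Appendix VII.** Add a job-satisfaction question, and ask staff what happened during delivery.

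**Cost.** A revised guide and a minor ethics amendment, with no extra interviews or staff. This applies only if interviews remain to be done.

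**If the interviews are complete.** Addendum item 4 refers to the Aim 2 interviews in the past tense, so this is possible. The sponsor should then file the guide actually used, if it differs from the appendices, or reconcile sections 8.2 and 8.3 with Appendices VI and VII. In either case the report should limit its qualitative mechanism claims to what the questions asked can support.
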